5.1.1 Primary Objective

To determine the safety and toxicity profile of BMX-001 in conjunction with RT and concurrent cisplatin chemotherapy for patients with locally advanced head and neck cancers.

5.1.2 **Secondary Objectives**

- 1) To assess the effect of BMX-001 in combination with RT and concurrent cisplatin in newly diagnosed HNSCC patients on overall survival (OS), progression free survival (PFS), and initial response to treatment.
- 2) To examine the impact on mucositis of BMX-001 in combination with RT and concurrent cisplatin in treatment of newly diagnosed patients with locally advanced head and neck cancers by evaluating the degree of oral mucositis at 30-39 Gy, 40-49 Gy, 50-59 Gy, and 60-70 Gy, the duration of oral mucositis, and evaluation of mucositis-related patient-reported outcomes.
- 3) To examine the impact on xerostomia of BMX-001 in combination with RT and concurrent cisplatin by evaluating degree of xerostomia at 30-39 Gy, 40-49 Gy, 50-59 Gy, and 60-70 Gy, the duration of xerostomia, and evaluation of xerostomia-related patient-reported outcomes.
- 4) To examine the impact on radiation dermatitis of BMX-001 in combination with RT and concurrent cisplatin at 30-39 Gy, 40-49 Gy, 50-59 Gy, and 60-70 Gy, the duration of radiation dermatitis, and evaluation of radiation dermatitis-related patient-reported outcomes
- 5) To characterize the single-dose and repeated-dose pharmacokinetic profiles of BMX-001 when delivered in combination with RT and concurrent cisplatin.

5.1.3 **Exploratory Objective**

 To describe patient-reported outcomes of health-related quality of life (HRQoL) in HNSCC patients treated with BMX-001 in combination with RT and concurrent cisplatin.

5.2 Phase 2 Endpoints

- 2) The primary endpoint is incidence of severe oral mucositis (grade 3 and 4).
- 3) The secondary endpoints are:
 - 1. Median duration (days) of severe oral mucositis)
 - 2. Median time (days) to onset of severe oral mucositis
 - 3. Incidence of grade >/= 2 Xerostomia at month 1 and 6 post completion of RT.

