9.7.1 Radiation Therapy / Adverse Events

Grade 3-4 (CTCAE, v. 4.03) therapy-induced mucositis and/or dysphagia, which are enhanced by cisplatin, are expected to develop in about two thirds of patients. Nutritional evaluation prior to the initiation of therapy for a prophylactic gastrostomy (PEG) tube placement is highly recommended. Placement of a feeding tube should be recorded, as should use of a feeding tube during and after treatment (e.g., greater than or less than 50% of nutrition by tube). Other common radiation adverse events include: fatigue, weight loss, regional alopecia, xerostomia, hoarseness, transient ear discomfort, dysgeusia, headaches, loss of appetite, and skin erythema and desquamation within the treatment fields.

Less common long-term treatment adverse events include: hypothyroidism, loss of hearing, chronic swallowing dysfunction requiring permanent feeding tube, and cervical fibrosis. Much less common radiation adverse events include: tissue necrosis, secondary cancer, mandibular osteoradionecrosis (< 5% incidence with attention to the standard dental recommendations), and cervical myelopathy (< 1% with restriction of spinal cord dose to \le 45 Gy).

Summary of possible side effects of radiation therapy to the head and neck:

COMMON, SOME MAY BE SERIOUS

In 100 people receiving radiation therapy, more than 20 and up to 100 may have:

- Sores in the mouth and/or throat which can be painful and make it very difficult to chew and or swallow foods
- Mouth dryness or changes in taste and/or smell that may be permanent
- Thick saliva
- Hoarseness
- Tanning or redness and/or irritation of the skin in the head and neck area being treated with radiation
- Ear pain and/or pressure
- Fatigue
- Weight loss
- Permanent hair loss in the area treated with radiation (face, chin, neck)
- Loss of teeth or cavities in the teeth if strict dental care is not followed and/or hypersensitivity of teeth

OCCASIONAL, SOME MAY BE SERIOUS

In 100 people receiving radiation therapy, from 4 to 20 may have:

- Decrease in function of the thyroid gland that may require you to take thyroid replacement medicine to prevent you from feeling tired or sleepy
- Serious damage to the jawbone, voice box, skin, or other parts of the head and neck that may require a major operation to correct and, rarely, can even be life threatening
- Temporary pain or scarring around nerves in the shoulder that could cause numbness and/or weakness
- Breathing problems

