- 3. To examine the impact on xerostomia of BMX-001 in combination with RT and concurrent cisplatin by evaluating degree of xerostomia at 30-39 Gy, 40-49 Gy, 50-59 Gy, and 60-70 Gy, the duration of xerostomia, and evaluation of xerostomia-related patient-reported outcomes.
 - The duration of xerostomia at 30-39 Gy, 40-49 Gy, 50-59 Gy, and 60-70 Gy, will be descriptively summarized using means and 95% confidence intervals (CIs). The

evaluation of xerostomia-related patient-reported outcomes at 30-39 Gy, 40-49 Gy, 50-59 Gy, and 60-70 Gy, will be descriptively summarized using frequencies, percentages, and 95% Cls.

4. To examine the impact on radiation dermatitis of BMX-001 in combination with RT and concurrent cisplatin by evaluating degree of radiation dermatitis at 30-39 Gy, 40-49 Gy, 50-59 Gy, and 60-70 Gy, the duration of radiation dermatitis, and evaluation of radiation dermatitis-related patient-reported outcomes.

The duration of radiation dermatitis at 30-39 Gy, 40-49 Gy, 50-59 Gy, and 60-70 Gy, will be descriptively summarized using means and 95% confidence intervals (CIs). The evaluation of radiation dermatitis-related patient-reported outcomes at 30-39 Gy, 40-49 Gy, 50-59 Gy, and 60-70 Gy, will be descriptively summarized using frequencies, percentages, and 95% CIs.

5. To characterize the single-dose and repeated-dose pharmacokinetic profiles of BMX-001 when delivered in combination RT and concurrent cisplatin.

16.1.5.4 **Exploratory Objectives for Phase 1 Study**

The mean change between baseline and each follow-up assessment for HRQoL will be descriptively summarized using means and 95% CIs.

16.2 Phase 2

16.2.1 **Primary Endpoint**

1) The primary endpoint is incidence of severe oral mucositis (grade 3 and 4).

The incidence rates of severe oral mucositis graded by CTCAE as grade 3 or 4 will be descriptively summarized and calculated.

- 2) The secondary endpoints are:
 - 1. Median duration (days) of severe oral mucositis
 - 2. Median time (days) to onset of severe oral mucositis
 - 3. Incidence of grade >/= 2 Xerostomia at month 1 and 6 post completion of RT.

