Kaplan-Meier methods will be used to graphically describe the distribution of overall survival (OS) and progression-free survival. OS is defined as the time interval between initiation of protocol treatment and death, with overall survival censored at last follow-up if the patient remained alive. PFS is defined as the time between initiation of protocol treatment and disease progression or death. If the patient remains alive without disease progression, then PFS will be censored at last follow-up. Median OS and PFS, as well as 6- and 12-month estimates of OS and PFS will be estimated from the Kaplan-Meier curve.

2. To assess radiographic response in locally advanced HNSCC patients treated with standard RT and cisplatin with BMX-001 at MTD.

The radiographic response (CR or PR) will be assessed as defined in 12.6.2. The radiographic response rate will be tabulated and reported using frequencies and 95% confidence intervals.

16.2.2.3 **Exploratory Objectives for Phase 2**

1. To further describe patient-reported outcomes of HRQoL in locally advanced HNSCC with standard RT, cisplatin, and BMX-001 at the MTD.

16.2.3 Interim Analysis for Phase 2

No interim efficacy analyses are planned given the length of time to assess an individual patient's outcome and the expected rapidity of patient accrual.

16.2.4 Sample Size Calculation for Phase 2

In this study, patients will receive BMX-001 at the Recommended Phase 2 Dose (RP2D). The ultimate goal of this study is to determine whether BMX-001 in combination with standard RT and cisplatin treatment is worthy of further investigation. The cohort will be compared with historical controls, which will be assessed for quality.

We will focus on the occurrence and severity of mucositis, xerostomia, and radiation dermatitis in this power calculation given that the study is not a randomized study, even though we are interested in comparing groups with respect to change in mucositis and xerostomia between protocol timepoints.

We anticipate accruing 48 patients which, for statistical purposes, we assume that approximately 40 will have available measurements of mucositis, xerostomia, and radiation dermatitis. We use a conservative estimate of a proportion of 0.50 since it results in the widest CI. A sample size of 40 produces a two-sided 95% exact confidence interval (Clopper-Pearson) with a width equal to 0.324 when the sample proportion is 0.50.

17 References

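### Two Phase 2 secondary endpoints are medians with no rule for patients who never have severe mucositis; cumulative incidence and mean days per treated patient would be more informative at little cost

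*Combined protocol and SAP*

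**What the plan says.** Section 5.2 names three Phase 2 secondary endpoints, and Section 16.2.1 repeats them:

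- "Median duration (days) of severe oral mucositis"
- "Median time (days) to onset of severe oral mucositis"
- "Incidence of grade >/= 2 Xerostomia at month 1 and 6 post completion of RT"

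The third is a proportion and is not at issue. The primary endpoint is the incidence of grade 3-4 oral mucositis.

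Nothing more is said about the two medians. No population, time origin or censoring rule is given, and nothing says whether unaffected patients are censored, counted as zero days or left out. The nearby analysis text helps only in part:

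- The opening of Section 16, repeated in 16.1.1, expects every treated patient to enter every analysis.
- Section 16.2.2.1 summarises mucositis duration by means with 95% CIs within dose bands. It does not use medians and does not single out severe grade.
- Section 16.2.2.2 assigns Kaplan-Meier to overall and progression-free survival only.
- Sections 16.2.2.1 and 16.2.4 plan a comparison with historical controls.

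On background rate, Section 9.7.1 says that grade 3-4 mucositis and/or dysphagia "are expected to develop in about two thirds of patients".

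**The concern.** A median describes a time or a duration well only when more than half of the group has the event. The drug is meant to make the event less common, from a background near two thirds, so the 50% line lies within the range of outcomes that the trial might see.

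Two readings of the endpoints are open, and each has a cost:

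- **All treated patients.** Below 50% cumulative incidence, the median onset is not reached and the median duration is exactly 0. An incidence of 0.45 and one of 0.25 then give the same pair of results.
- **Affected patients only.** The group summarised is defined by the primary endpoint, so its make-up shifts with the drug's effect. In a single-arm comparison with historical controls, no concurrent arm would reveal that shift.

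Without a stated rule, the choice between these readings could be made after the open-label data are known.

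**Working it through.** **1. The plan's own figure.** Section 16.2.4 states a "two-sided 95% exact confidence interval (Clopper-Pearson) with a width equal to 0.324 when the sample proportion is 0.50" for 40 patients. The Clopper-Pearson limits for x = 20, n = 40 are the 0.025 quantile of Beta(20, 21) and the 0.975 quantile of Beta(21, 20). These are 0.338 and 0.662, width 0.324. The figure reproduces.

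**2. Inputs.**
- Evaluable patients: 40 of 48 (Section 16.2.4: "we assume that approximately 40 will have available measurements of mucositis, xerostomia, and radiation dermatitis").
- Background incidence: at most about 2/3 (Section 9.7.1). That figure covers mucositis and/or dysphagia, so the rate for mucositis alone can only be equal or lower.
- 0.50: Section 16.2.4 says "We use a conservative estimate of a proportion of 0.50 since it results in the widest CI". It is a precision convention, not an expected or target rate.

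**3. Distance to the 50% line.** The relative reduction from 2/3 to 0.50 is 1 − 0.50/(2/3) = 25%.

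**4. Chance that fewer than half are affected.** With no early censoring and X ~ Binomial(n, p), this is P(X ≤ 19) for n = 40 and P(X ≤ 23) for n = 48.

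| True incidence | n = 40 | n = 48 |
|---|---|---|
| 2/3 | 1.0% | 0.6% |
| 0.60 | 7.4% | 6.0% |
| 0.55 | 21.3% | 20.0% |
| 0.50 | 43.7% | 44.3% |
| 0.45 | 68.4% | 71.0% |
| 0.40 | 87.0% | 89.7% |

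The values between 2/3 and 0.40 are assumed scenarios. With early censoring, the threshold applies to the Kaplan-Meier estimate and not to the crude proportion.

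**5. A worked illustration (assumed data).** Of 40 patients, 24 are affected, with durations evenly spaced from 7 to 56 days (step 49/23 = 2.13). The drug prevents the 10 shortest episodes and leaves the rest unchanged.

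| Summary | Before | After |
|---|---|---|
| Affected-only median | (7 + 56)/2 = 31.5 days | (28.3 + 56)/2 = 42.2 days |
| All-patient median | (13.4 + 15.5)/2 = 14.5 days | 0 (26 of 40 are zeros) |
| Mean days per treated patient | 24 × 31.5/40 = 18.9 | 14 × 42.15/40 = 14.8 |

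The affected-only median moves the wrong way. The all-patient median moves the right way but reaches its floor. The mean moves the right way and still has room to fall.

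**6. Does the affected-only result depend on the mechanism?** Two assumed models were compared, each with incidence falling from about 0.667 to about 0.40.
- *Latent severity.* Worse cases start earlier and last longer, and the drug prevents the mildest. Affected-only median duration rises from 25.6 to 30.5 days, and is still 27.4 if every remaining episode is 10% shorter. Affected-only median onset moves earlier, from day 32.5 to day 30.3. Mean days per treated patient falls from 19.0 to 13.3.
- *Proportional hazards.* The hazard is constant from day 14 to day 56, with no variation between patients. Affected-only median onset moves later, from day 29.5 to day 32.4.

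So reversal can occur but need not.

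**The case against.** The strongest reply is that nothing here is wrong. A median duration of 0 says that at least half of patients had no severe mucositis, and an onset median that is not reached is a familiar, favourable result. Prevention is already captured by the primary endpoint. Section 16.2.2.1 adds mean durations by dose band. The medians carry no test, alpha or decision rule. Under moderate benefit they usually survive: at a true incidence of 0.60 or 0.55, at least half of 40 patients are affected 92.6% or 78.7% of the time.

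Most of this stands, and it rules out some stronger readings that a reader might infer:

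- *The medians are lost whenever the drug works.* They are lost only when cumulative incidence falls below 50%, which from 2/3 needs a relative reduction of more than 25%.
- *The medians are safe if the drug does nothing.* The 1.0% figure uses the combined mucositis and/or dysphagia rate. The documents give no rate for mucositis alone, so 2/3 is an upper bound and 1.0% is a best case.
- *The 43.7% describes the expected scenario.* It does not, because 0.50 was chosen only for the widest interval.
- *Affected-only medians will mislead.* That depends on which cases the drug prevents, and no section addresses this.

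What the reply does not answer is the silence on unaffected patients. The dose-band means do not fill that gap, since they neither isolate severe grade nor say that unaffected patients count as zero.

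**Conclusion.** The point holds as a low-cost improvement. The two medians are legitimate but underspecified, and they lose gradation in part of the range where the drug would be helping. On the all-patient reading with 40 evaluable patients, the chance of that loss runs from 1.0% at an incidence of 2/3 to 87.0% at 0.40, assuming no early censoring. On the affected-only reading the medians condition on the primary outcome, and their direction under benefit depends on a mechanism that the documents do not give.

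The documents do not support calling the endpoints invalid. The all-patient versions point the right way, the endpoints are descriptive, and the primary endpoint and its stated interval width are unaffected.

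**What to change.** In Sections 5.2 and 16.2.1:

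- **Onset.** Report a Kaplan-Meier or cumulative-incidence curve for first grade 3-4 oral mucositis in all treated patients, from a stated time origin. Give estimates and 95% CIs at fixed radiotherapy times, for example the end of weeks 4 and 6 and the end of radiotherapy. Give the median if it is reached.
- **Duration.** Report mean days of grade 3-4 mucositis per treated patient, counting 0 for unaffected patients, with a bootstrap 95% CI. This also fits the means already planned in Section 16.2.2.1.
- **Medians.** Keep both as supportive summaries, state the population for each, and label any affected-only median as conditional on having severe mucositis.

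The cost is wording and a little more analysis. No new visits are needed, because Section 13.1.5 already has mucositis graded weekly during therapy and at clinic visits afterwards. A short rule is needed for turning those grades into days and for episodes unresolved at the last assessment; the medians need the same rule. The main downside is that historical reports may give only medians, which is the reason to keep them.

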5.3 Phase 2 Objectives

 To confirm the safety and tolerability of the MTD of BMX-001 in conjunction with RT and concurrent cisplatin in a cohort of newly diagnosed patients with locally advanced head and neck cancers.

2) To further explore efficacy based on the impact of BMX-001 on mucositis, xerostomia, and radiation dermatitis in treatment of newly diagnosed patients with locally advanced head and neck cancers by evaluating the degree of these adverse events at 30-39 Gy, 40-49 Gy, 50-59 Gy, and 60-70 Gy, the duration of the adverse events, and evaluation of related patient-reported outcomes.

5.3.1 **Secondary Objective**

- 1) To assess the efficacy of BMX-001 at the MTD in a cohort of HNSCC patients based upon overall survival (OS), median progression free survival (PFS), and initial response to treatment.
- 2) To assess radiographic response in locally advanced HNSCC patients treated with standard RT and cisplatin with BMX-001 at the MTD.

5.3.2 **Exploratory Objectives**

3) To further describe patient-reported outcomes of HRQoL in locally advanced HNSCC with standard RT, cisplatin, and BMX-001 at the MTD.

6 Patient Selection

6.1 Inclusion Criteria

- Pathologically confirmed (histologically or cytologically) diagnosis of squamous cell carcinoma of the oropharynx, larynx, hypopharynx, nasopharyngeal, or oral cavity with clinical or pathologic high-risk features for whom cisplatin and radiation would be considered appropriate care.
- 2) Treatment plan to receive a continuous course of IMRT delivered as single daily fractions of 2.0 to 2.1 Gy with a cumulative radiation dose between 60 Gy and 70 Gy depending on whether patients are considered post-operative high risk or unresectable/organ preservation high risk. Planned radiation treatment fields must include at least two oral sites buccal mucosa, retromolar trigone, floor of mouth, oral tongue, soft palate, hard palate) with a portion of each site receiving a minimum total of 50 Gy.
- 3) Patients who are to undergo definitive chemoradiation must have clinically or radiographically evident measurable disease at the primary site and/or at nodal stations. Tonsillectomy or local excision of the primary without removal of nodal disease is permitted, as is excision removing gross nodal disease but with intact primary site.
- 4) Limited neck dissections retrieving ≤ 4 nodes are permitted and considered as non-therapeutic nodal excisions. Fine needle aspirations of the neck that are positive for squamous cell carcinoma are sufficient for diagnosis pending pathology review at participating institutions.
- 5) For patients undergoing curative intent resection the following criteria are required:
 - Pathologically (histologically or cytologically) proven diagnosis of head and neck squamous cell carcinoma
 - Patients must have undergone gross total surgical resection within 42 days prior to registration and beginning of therapy under the clinical trial. Note: Patients may have biopsy under general anesthesia in an operating room followed by definitive ablative cancer surgery representing gross total resection.
- 6) Clinical or pathologic stage Stage III-IVB per AJCC, 7th edition.
- 7) General history and physical examination by a radiation oncologist and medical oncologist within 4 weeks prior to enrollment.
- 8) Examination by an ENT or head and neck surgeon, including laryngopharyngoscopy (mirror and/or fiberoptic and/or direct procedure) within 8 weeks prior to enrollment.
- 9) Axial imaging of the neck and chest- CT, MRI and/or PET/CT is acceptable, within 8 weeks prior to date of consent.
- 10) Age \geq 18 years.
- 11) Zubrod Performance Status 0-2 within 4 weeks prior to enrollment.
- 12) CBC/differential obtained within 2 weeks prior to starting the study drug with adequate bone marrow function, defined as follows:
 - Hemoglobin ≥ 9.0 g/dl;
 - Platelets ≥ 100,000 cells/mm³;
 - Absolute neutrophil count (ANC) > 1,500 cell/mm³.

- 13) Adequate hepatic function as defined as follows:
 - Total bilirubin < 2x institutional ULN within 2 weeks prior to starting the study drug;
 - AST and ALT <3x institutional ULN within 2 weeks prior to starting the study drug.
- 14) Adequate renal function defined as follows:
 - Serum creatinine < 1.5 mg/dl within 2 weeks prior to starting the study drug or creatinine clearance rate (CCr) ≥ 50 mL/min within 2 weeks prior to starting the study drug determined by 24-hour collection or estimated by Cockcroft-Gault formula:
 - \circ CCr male = [(140 age) x (wt in kg)]/[(Serum Cr mg/dl) x (72)]
 - CCr female = 0.85 x (CrCl male)
- 15) Patient must be willing and able to follow study procedures and instructions.
- 16) Patient must provide study-specific informed consent within 28 days prior to starting the study drug.
- 17) Negative pregnancy test for women of child-bearing potential within 48 hours prior to first dose of BMX-001.
- 18) Women of childbearing potential and male participants must agree to use a medically effective means of birth control throughout their participation in the treatment phase of the study and until 12 months following the last study treatment.

6.2 Conditions for Patient Ineligibility (Exclusion Criteria)

- 1) Stage I or II; T1N1 and T2N1 stage III presentations per AJCC 7th edition
- 2) Distant metastasis
- 3) Hypertension requiring 3 or more anti-hypertensive medications to control
- 4) Grade ≥2 hypotension at screening
- 5) Requirement for concurrent treatment with nitrates or other drugs that may, in the judgment of the treating investigator, create a risk for a precipitous decrease in blood pressure
- 6) History of syncope within the last 6 months
- 7) Patients receiving, or unable to stop use at least 1 week prior to receiving the first dose of BMX-001, medications listed in Section 12.2 of the protocol are not eligible.
- 8) Pregnancy or women of childbearing potential and men who are sexually active and not willing/able to use medically acceptable forms of contraception; this exclusion is necessary because the treatment involved in this study may be significantly teratogenic
- 9) Women who are breast feeding are not eligible
- 10) Prior allergic reaction to cisplatin
- 11) Known hypersensitivity to compounds of similar chemical composition to BMX-001
- 12) Grade 3-4 electrolyte abnormalities (CTCAE v 4.03) except sodium, which must be ≥126 mmol/L.
- 13) Prior unrelated malignancy requiring current active treatment with the exception of cervical carcinoma *in situ*, basal cell carcinoma of the skin, resected T1-2N0M0 differentiated thyroid cancers, invasive cancers with a 3-year disease-free interval, Ta bladder cancers, or low and favorable intermediate risk prostate cancer.
- 14) Prior history of HNSCC receiving radiation or chemo-radiation.

- 15) Prior systemic chemotherapy for the study cancer (including neoadjuvant chemotherapy); note that prior chemotherapy for a different cancer is allowable.
- 16) Prior radiotherapy that would result in overlap of radiation treatment fields with planned treatment for study cancer.
- 17) A marked baseline prolongation of QT/QTc interval (e.g., repeated demonstration of a QTc interval >480 milliseconds (ms) (CTCAE grade 1) using the specific/usual choice by clinical center for correction factor.
- 18) A history of additional risk factors for Torsades de Pointes (e.g., congestive heart failure, hypokalemia, known family history of Long QT Syndrome).
- 19) Severe, active co-morbidity, defined as follows:
 - Cardiovascular disease or cerebrovascular disease, for example cerebrovascular accidents or myocardial infarction ≤ 6 months prior to study enrollment, unstable angina, New York Heart Association (NYHA) Grade II or greater congestive heart failure (CHF), or serious cardiac arrhythmia uncontrolled by medication or with the potential to interfere with protocol treatment;
 - Significant vascular disease (e.g., aortic aneurysm requiring surgical repair or recent arterial thrombosis) within 6 months prior to enrollment;
 - History or evidence upon physical/neurological examination of central nervous system disease (e.g., seizures) unrelated to cancer unless adequately controlled by medication;
 - Acute bacterial or fungal infection requiring intravenous antibiotics within 7 days of enrollment;
 - Chronic Obstructive Pulmonary Disease exacerbation or other respiratory illness requiring hospitalization or precluding study therapy within 30 days of registration;
 - Patients known to be HIV positive or have active viral hepatitis.

7 Pretreatment Evaluations/Management

